Statistical Analysis	
Sample Size Calculation:
 
A systematic review and meta-analysis was performed and resulted in selecting a performance goal (PG) of 80%. A sample size of 120 subjects is necessary to achieve at least 80% power for demonstrating that the Technical Efficacy rate of the NeuWave Certus Microwave Ablation System is > 80% when the expected performance is 90%, and a one-sided significance level of 0.025 is used with the Normal Approximation to the Binomial distribution, with adjustment for 10% dropout. Each site will enroll 2 subjects first in the run-in phase besides the 120 subjects. In view of the lack of available clinical data for evaluating the performance of the study product in percutaneous lung tumor ablation procedure, the sample size will be re-estimated adopting a self-adaptive method after approximately 50% of the initial planned sample size are enrolled.
 
Statistical analysis of study endpoints:
 
The number and percentage of tumors achieving Technical Efficacy will be summarized and corresponding 95% confidence intervals will be estimated. If the lower limit of the 95% CI of the Technical Efficacy Rate is higher than the predefined PG value, primary endpoint success will be concluded.
 
The Technical Success Rate, A0 Ablation Rate, Re-Ablation Technical Success Rate will be summarized in a similar way.

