existing literature, and then the point estimate and corresponding 95% confidence interval were estimated by meta-analysis using random effects. The meta-analysis results showed that, prior studies based on a variety of populations have a mean Technical Efficacy rate of 87% (95%CI: 79%-92%) after MWA of lung cancer at 1 month. Considering that PG is the minimum threshold of the acceptable performance, new product-related study curve, clinically significant Technical Efficacy rate, and lower limit of the above 95% confidence interval, the PG of the study is set as 80%. The primary analysis of Technical Efficacy will be performed at the Target Tumor level and at the subject level on the Full Analysis Set. For multi-target-tumor subjects, the largest Target Tumor, determined by the maximum three dimensions of each target tumor, will be used for the subject-level analysis. This will be repeated for the Per Protocol Set.

An additional analysis will be conducted based on the investigators evaluation of Technical Efficacy Rate.

- **Secondary endpoints:**

1. The number and percentage of tumors with Technical Success Rate, A0 Ablation Rate, and Re-ablation Technical Success Rate will be summarized and 95% confidence interval will be estimated based on the Normal Approximation to the Binomial distribution.
 - Technical Success Rate and A0 Ablation Rate will be based on ablation zone tumor coverage and the ablation margin achieved after the first ablation and prior to any repeat ablations.
 - Re-Ablation Technical Success Rate will be based on ablation zone tumor coverage and ablation margin achieved after re-ablation.
2. Local Tumor Progression will be estimated using Kaplan-Meier method and 95% confidence interval will be provided.
3. Progression-Free Survival and Overall Survival will be estimated based on patient level using Kaplan-Meier method and 95% confidence interval will be provided.
4. The summary description of pain scores, ECOG scores and Quality of Life scores will be reported based on patient level according to the standard recommended method.
5. The length of stay as well as the number and percentage of readmissions will be described based on the patient level, and the reasons for readmission will be counted and percentage will be calculated.
6. Ablation Procedure Related Indicators will be reported descriptively.

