## 7 Sample Size Calculation

This study plans to enroll 120 subjects plus run-in subjects (each site will enroll 2 run-in subjects). The sample size calculation is justified as follows:

The study sample size is determined by hypothesis testing for the comparison of the primary endpoint versus the performance goal (PG). The study's PG is set as 80%. The primary hypothesis test of the primary endpoint is:  $H_0: P \leq P_0$  (80%) vs.  $H_1: P > 80\%$ , where  $P$  is the actual Technical Efficacy Rate of the Neuwave Certus Microwave Ablation System. A sample size of 120 subjects is necessary to achieve at least 80% power for demonstrating that the Technical Efficacy rate of the NeuWave Certus Microwave Ablation System is  $> 80\%$  when the expected performance is 90% and a one-sided significance level of 0.025 is used with the Normal Approximation to the Binomial distribution (Z-test that uses  $S(P_0)$  to estimate the standard deviation), with adjustment for up to 10% dropout.

Each site will enroll 2 subjects first in the run-in phase. So the total sample size will be 120 subjects plus run-in subjects (each site will enroll 2 run-in subjects).

Of the 120 non run-in sample, the number of cases for either disease type is limited at up to 75% (i.e., in the 120 non run-in sample, up to 90 subjects could be NSCLC or oligometastatic lung tumor).

In addition, given the lack of available clinical data for the evaluation of the performance of the investigational product in pulmonary tumor ablation procedures, an adaptive approach will be used to re-estimate the sample size as per the "promising zone" method of Mehta and Pocock (2011) after 50% of the target enrolled subjects complete the Visit 3 Technical Efficacy Evaluation. This procedure involves evaluation of the conditional power (CP) in the interim analysis. If the CP is to fall in the pre-specified "promising zone", the sample size will

be increased to boost the CP up to the target level of 80% for the primary effectiveness endpoint, in the meanwhile, the new sample size will be subject to a predefined maximum value (200 enrolled subjects). If the CP is to fall out of the pre-specified “promising zone”, the study will maintain the originally planned sample size, i.e. 120 subjects plus run-in subjects. For details in sample size re-estimation method, please refer to Section 8.12.

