## **8.9 Primary Endpoint and Associated Hypotheses**

Analyses will be conducted on the FAS, PPS, and run-in set.

The primary efficacy endpoint is Technical Efficacy Rate, defined as the percentage of tumors that are completely covered by the ablation area without signs of pathological enhancement as assessed by lung enhanced CT at Visit 3 (i.e., 30 days $\pm$ 7 days after the first ablation). Each subject will have a maximum of one NSCLC tumor or a maximum of three ipsilateral oligometastatic lung tumors to be ablated, each of which will be defined as a success or failure. If the initial ablated tumor had re-ablation before Visit 3 Technical Efficacy assessment, the re-ablated tumor will be considered as a failure. The re-ablation will not change or extend the subject's follow-up schedule. Technical Efficacy Rate will be analyzed based on both the target tumor level and subject level.

The Technical Efficacy Rate is assessed by both the study physician (i.e., PI) and Independent Central Imaging Committee (IRC). Primary statistical analysis and hypothesis testing for the primary effectiveness endpoint will be based on IRC's evaluation results. For IRC evaluation, there will be at least two reviewers providing their results. If the two reviewer's results are the same, the first one's result will be used. If the two reviewer's results differ, a third reviewer will evaluate and his or her result will be used for the analysis. This analysis rule will be applied for all IRC-based endpoint.

The null and alternative hypotheses for primary analysis of the primary endpoint are as follows:

$$H_0: P \leq P_0 (80\%)$$

$$H_1: P > 80\%,$$

where P is the actual Technical Efficacy Rate using the NeuWave Certus Microwave Ablation System.

If the initial ablated tumor had re-ablation before the Visit 3 Technical Efficacy assessment, the re-ablated tumor will be considered as a failure. Other tumors with missing parameters or other early discontinuations will not have data imputation.

For multi-target-tumor subjects, his or her largest Target Tumor, determined by the maximum three dimensions of each target tumor, will be used for subject-level analysis conservatively.

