The number and proportion of tumors/subjects achieving Technical Efficacy at Visit 3 will be summarized and the corresponding 95% CI based on the Normal Approximation to Binomial Distribution (Z-test that uses S(P0) to estimate the standard deviation) or Clopper-Pearson method (if the proportion is greater than 90%) will be calculated.

The success criterion of the primary effectiveness endpoint will be met if the lower limit of the two-sided 95% CI for Technical Efficacy Rate is higher than 0.8.

The following additional sensitivity analyses will be conducted for the primary effectiveness endpoint using same statistical method:

- Sensitivity analysis 1: based on the PP population at both the target tumor level and subject level.
- Sensitivity analysis 2: based on the FAS and different imputation rule for missing data of the primary effectiveness endpoint (see in Section 8.14) at both the target tumor level and subject level.

Additional analysis: based on the FAS and primary effectiveness endpoint values assessed by the investigator at the target tumor level.

Listings, including IRC assessment and PI assessment, will be provided.

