## **8.12 Plans for Interim Analysis**

No interim analyses are planned for the purpose of stopping the study early for success or futility.

An interim analysis for study sample size re-estimation per the observed Technical Efficacy Rate will be performed after 50% of the target enrolled subjects complete the Visit 3 (at least  $n_1=54$  evaluable subjects with primary effectiveness endpoint data). To warrant the originally intended 80% power of the study at the 0.025 level (1-sided), the sample size may be increased to a maximum of 200 enrolled subjects in order to provide 180 evaluable subjects, given the expected dropout rate.

The sample size re-estimation method is based on evaluation of conditional power in relationship to pre-specified decision criteria defined by ranges of attainable conditional power values. Only an increase in sample size is possible under this approach when observed conditional power falls within the 'promising zone' as described below (Bhatt 2016, Chen 2004, Cui 1999, Mehta and Pocock 2011, Orloff 2009).

The independent statistician will review the conditional power, and make a recommendation per pre-specified criteria about the sample size increasing or maintaining the originally planned sample size.

The sponsor is not allowed to access the interim results prior to the primary analysis.

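### The primary success rule does not say whether the tumour-level rate, the subject-level rate or both must pass, and the tumour-level interval ignores clustering, so the one-sided 0.025 level is not guaranteed

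*SAP*

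**What the plan says.** **Level of analysis.** SAP 8.9 defines the endpoint as a percentage of tumours and adds: "Technical Efficacy Rate will be analyzed based on both the target tumor level and subject level". At subject level, only the largest target tumour of a multi-tumour subject counts. Protocol 8.1 makes both levels primary: "The primary analysis of Technical Efficacy will be performed at the Target Tumor level and at the subject level on the Full Analysis Set".

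**Success rule.** SAP 8.9 states: "The success criterion of the primary effectiveness endpoint will be met if the lower limit of the two-sided 95% CI for Technical Efficacy Rate" is above 0.8. No level is attached. The sentence on estimation covers both units: "The number and proportion of tumors/subjects achieving Technical Efficacy at Visit 3 will be summarized". Protocol 8.3 has the same single rule and also names no level. In the protocol synopsis, the sentence just before the success rule concerns tumours: "The number and percentage of tumors achieving Technical Efficacy will be summarized and corresponding 95% confidence intervals will be estimated".

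**Interval.** SAP 8.9 uses the normal approximation with the standard deviation taken at P0, or the "Clopper-Pearson method (if the proportion is greater than 90%) will be calculated". Neither document mentions a design effect, a robust variance or any other allowance for several tumours in one subject.

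**Planning unit.** SAP 7 counts subjects: "A sample size of 120 subjects is necessary to achieve at least 80% power". SAP 8.12 sets the interim look at 54 "evaluable subjects with primary effectiveness endpoint data", but 8.12.1 does not say at which level the interim rate and z1 are computed.

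The SAP takes precedence over the protocol's statistical section where they differ, but it does not settle this point.

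**The concern.** One hypothesis with one P is tested on two different rates, and the plan does not say what follows if they disagree. This rule decides trial success and the regulatory submission. If the level is chosen after the primary results are seen, the choice is data-driven.

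The endpoint definition and the synopsis lean towards the tumour level. That is the level at which the planned interval treats up to three tumours in one patient, ablated in a single procedure, as independent. If outcomes within a patient are positively correlated, the interval is too narrow and the test rejects too often.

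**Working it through.** **Inputs from the documents.** P0 = 0.80, expected rate 0.90, one-sided 0.025, 10% dropout, 120 enrolled and 108 evaluable subjects, interim at 54, cap of 180 evaluable (SAP 7, 8.12). One tumour per NSCLC subject and up to three per oligometastatic subject (SAP 8.9). Neither disease type may exceed 75%, so the oligometastatic share lies between 25% and 75% (SAP 7).

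**Assumptions, not in the documents.** Oligometastatic subjects have 1/2/3 tumours in 60/25/15%, or in one third each. The within-subject correlation (ICC) is 0, 0.2 or 0.5.

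**Step 1: reproduce the plan.** n = [(1.960×√0.16 + 0.842×√0.09)/0.10]² = [(0.784 + 0.2525)/0.10]² = 107.4, so 108; 108/0.9 = 120. The figure reproduces with one observation per subject. The pass mark is 0.80 + 1.96×√(0.16/108) = 0.8754, so at least 95 of 108. Exact binomial: error 0.0210 at P = 0.80, power 0.810 at P = 0.90.

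**Step 2: a split result.** Take both observed rates at 87.0%, the plan's own meta-analysis mean.
- Subjects, 94/108: SE = √(0.16/108) = 0.0385; z = 0.0704/0.0385 = 1.83; lower limit 0.870 − 0.075 = 0.795. Fails.
- Tumours, 141/162: SE = √(0.16/162) = 0.0314; z = 0.0704/0.0314 = 2.24; lower limit 0.870 − 0.062 = 0.809. Passes.

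The tumour-level pass is lost once the design effect exceeds (2.24/1.96)² = 1.31. For illustration, if 27 subjects had three tumours each and 81 had one (162 tumours), the design effect would be 1 + ICC×(27×6)/162 = 1 + ICC, so an ICC above 0.31 would reverse the verdict.

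**Step 3: size of the clustering effect.** D = 1 + ICC×Σm(m−1)/Σm, with m the number of tumours per subject.
- Smallest case (25% oligometastatic, 60/25/15): per subject, Σm = 0.75 + 0.25×1.55 = 1.1375 (123 tumours) and Σm(m−1) = 0.25×(0.25×2 + 0.15×6) = 0.35. At ICC 0.2, D = 1 + 0.2×0.308 = 1.06.
- Largest case (75%, one third each): Σm = 0.25 + 0.75×2 = 1.75 (189 tumours) and Σm(m−1) = 0.75×(2 + 6)/3 = 2.0. At ICC 0.5, D = 1 + 0.5×1.143 = 1.57. The approximate error is 1 − Φ(1.96/√1.57) = 5.9%; simulation gives 5.3%.

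**Step 4: type I error by reading.** Beta-binomial simulation, 108 subjects, true rate 0.80 at both levels, SAP 8.9 intervals, 20,000 trials per scenario (Monte Carlo SE about 0.1 point near 3%):

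| Deciding rule | ICC 0 | ICC 0.2 | ICC 0.5 |
|---|---|---|---|
| Subject level alone (exact) | 2.1% | 2.1% | 2.1% |
| Tumour level, planned interval | 2.1–2.2% | 2.3–3.4% | 3.0–5.3% |
| Either suffices | 2.8–3.5% | 2.9–4.4% | 3.4–6.0% |

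Requiring both gives 0.8–1.8% over all scenarios. If the single or largest tumour has a true rate 5 points below the others, with the tumour-level rate at 0.80, the either-suffices row becomes 2.3–2.5%, 2.6–3.7% and 2.8–5.5%.

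A separate simulation (200,000 trials per scenario, 1/2/3 tumours in 50/30/20%, half the subjects oligometastatic, about 146 tumours) gives a tumour-level error of 2.2%, 2.8%, 4.0% and 5.2% at ICC 0, 0.2, 0.5 and 0.8. At the extreme of 75% oligometastatic with three tumours each, it is 4.7% at ICC 0.2 and 8.0% at ICC 0.5. Requiring both stays at 0.6–2.0% throughout.

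**Step 5: re-estimation.** With the 54/108/180 scheme and the SAP 8.12.1 formula, the Step 4 ranges barely move: tumour level 1.9–2.4%, 2.2–3.4% and 2.9–5.4% by ICC; either 2.5–6.0%; subject level 1.9–2.2%; both 0.8–1.6%.

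**Step 6: how often the levels disagree.** At the planned P = 0.90 they give opposite verdicts in 7.9–16.8% of trials.

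**The case against.** The best reply is that the plan does point somewhere. The rate is defined per tumour, and the success rule uses that defined term. Protocol 8.1 counts successes by tumour before stating the hypotheses. The investigator-read analysis and the subgroup analyses are at tumour level. Alternatively, both documents speak of tumour and subject level together, so both must pass, a split is a failure, and the level is kept. These pointers are real, but they lead to different rules. Protocol 8.1 does treat both levels as primary, and neither document says in words that both must pass. The tumour-level reading leads straight to the unadjusted interval.

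Several narrower objections stand.
- Nothing in the text says that passing either level is enough, so that row of the table is hypothetical.
- The documents do not support an ICC as high as 0.5. At low ICC with few multi-tumour subjects, the tumour-level error stays near 2.5%.
- The frequency of opposite verdicts mainly reflects the larger number of tumours, which gives the tumour-level test more power. It measures the cost of not naming the level and is not inflation of type I error.

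**Conclusion.** The concern holds. That no deciding level is named, and that the tumour-level interval ignores clustering, can both be read from the text without any assumption. As written, the rule cannot adjudicate a split result.

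The 0.025 level is kept if the subject level alone decides, and it was kept in every scenario simulated if both must pass. It is exceeded if the tumour level decides with the planned interval and the within-subject correlation is material: by up to about 1 point at ICC 0.2 and up to about 3 points at ICC 0.5 in the main scenarios, and by more if multi-tumour subjects mostly have three tumours. These sizes rest on assumed ICC and tumour counts, so the supportable statement is that the level is not guaranteed. The interim gap is smaller: the count is clearly in subjects, and only the level of the interim rate is left open. This should be fixed before the primary results are unblinded.

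**What to change.** State one decision rule in SAP 8.9, on the FAS with the IRC read, before the database lock for the primary analysis. Any of three would do:

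1. **Subject level decides.** This matches the subject-based 108 (error 0.021, power 81%).
2. **Both levels must pass.** Restate power as about 78–81% (simulated 78.1–80.6%), at most about 3 points below 81%.
3. **Tumour level decides, with a cluster-adjusted variance.** This matches the per-tumour endpoint (simulated error 1.9–2.5%, power 78–96%, the low end at ICC 0.5).

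Whichever is chosen, compute tumour-level intervals with subject as the cluster. For ICC 0.2–0.5 this widens them by about 3–25% (√1.06 = 1.03, √1.57 = 1.25). It is essential for the primary endpoint and good practice for the descriptive secondary rates. In SAP 8.12, say that the interim rate and z1 use the level of the deciding test.

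An optional addition is a supportive subject-level rate that counts a subject as a failure if any target tumour fails, because the largest-tumour rule leaves out failures in smaller tumours. The verdict does not depend on it.

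The cost is SAP wording and one extra variance calculation. Options 1 and 2 need no new data or patients.

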8. STATISTICAL CONSIDERATIONS

8.1. Statistical Design, Method and Analysis Procedure

This study is a single-arm, prospective, multi-center clinical study with performance goals.

Categorical variables will be summarized descriptively by frequencies and associated percentages. Continuous variables will be summarized descriptively by number of subjects, mean, standard deviation, median, quartile, minimum, and maximum.

All endpoint analyses at the tumor level will be conducted on “Target Tumors” (i.e. tumors identified to be ablated during screening and receive ablation power during the initial ablation procedure).

The data analysis plan will be documented in detail in the Statistical Analysis Plan (SAP).

- **Primary Effectiveness Endpoint-Technical Efficacy Rate**

The analysis of the primary effectiveness endpoint is to demonstrate the technical effectiveness of the NeuWave Certus microwave ablation system and accessories in the ablation of Chinese patients with NSCLC or secondary lung cancer. This endpoint will be based on the scan obtained at Visit 3 and will count as successes when tumors with completely covered ablation zone without pathological enhancement as assessed by enhanced CT scan at Visit 3 (i.e., 30 days \pm 7 days after the first ablation procedure). Additionally, if an initial ablated tumor had re-ablation before the Visit 3 Technical Efficacy assessment, the re-ablated tumor will be considered a failure.

The primary endpoint will be assessed based on an independent review committee (IRC)’s evaluation results using the following methods:

The hypothesis test for Technical Efficacy Rate is null hypothesis (H_0): $P \leq P_0$ (80%) vs. alternative hypothesis (H_1): $P > 80\%$. Wherein, P represents the true technical efficiency for the NeuWave Certus Microwave Ablation System and 80% is the Performance Goal (PG). If the lower limit of the 95% CI of the Technical Efficacy rate based on the Normal Approximation to the Binomial distribution (Z-test that uses $S(P_0)$ to estimate the standard deviation) is higher than the predefined PG value, primary endpoint success is considered.

PG is determined based on the results of the meta-analysis on the existing literature of similar techniques. The Technical Efficacy rate at 1 month after microwave ablation was extracted from

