### **8.12.1 Conditional Power**

Conditional power refers to the probability of concluding a positive study at the end of trial, given interim results of treatment effect and the assumed true treatment effect. The conditional power at the interim analysis  $CP_{\hat{\delta}_1}(z_1, \tilde{n}_2)$  can be defined by the following equation from Mehta and Pocock (2011):

$$CP_{\hat{\delta}_1}(z_1, \tilde{n}_2) = 1 - \Phi\left(\frac{z_\alpha \sqrt{n_2} - z_1 \sqrt{n_1}}{\sqrt{\tilde{n}_2}} - \frac{z_1 \sqrt{\tilde{n}_2}}{\sqrt{n_1}}\right)$$

Where  $\tilde{n}_2 = n_2 - n_1$ ,  $z_\alpha = \Phi^{-1}(1 - \alpha)$ , and  $z_1$  is the value of test statistic as computed at the interim analysis and  $Z_1 = \frac{P_1 - P_0}{\sqrt{P_0 \times (1 - P_0)/n_1}}$ . Define the observed interim estimate,  $\hat{\delta}_1 = \hat{p}_1 - p_0$ , where  $\hat{p}_1$  is Technical Efficacy Rate observed at interim analysis and  $p_0$  is the PG.

Our targeted conditional power at the first interim review is 0.80 (i.e., same as the study power), and we pre-specify a range of conditional power values below 0.80 that would deem our interim results promising and warrant a sample size re-estimation. The “promising zone” for conditional power was defined as between 0.387 and 0.80, as per Mehta and Pocock (2011) method using one-sided alpha of 0.025 and power of 0.80. We propose the following criteria for sample size increase, depending on the zone into which  $CP_{\hat{\delta}_1}(z_1, \tilde{n}_2')$  falls at the interim look.

- Favorable zone: If  $CP \geq 0.8$  (or equivalently  $z_1 \geq 1.806$ ), continue to  $n_2 = 108$
- Promising zone: If  $0.387 \leq CP < 0.8$  (or equivalently  $1.243 \leq z_1 < 1.806$ ) increase sample size to  $n_2^* = \min(n_2', n_{max})$ , where  $n_2'$  is such that  $CP = 0.8$
- Unfavorable zone: If  $CP < 0.387$  (or equivalently  $z_1 < 1.243$ ), continue to  $n_2 = 108$

The following table provide the parameters used for the sample size re-estimation.

Design parameters	Value
Interim Sample Size, $n_1$	54
Cumulative Final Sample Size, $n_2$	108
Incremental Sample Size, $\tilde{n}_2$	54
Pre-specified Maximum Allowable Sample Size, $n_{max}$	180
Drop-out rate	10%
Significance Level (Alpha)	0.025 (one-sided)
Re-Estimated Cumulative Final Sample Size, $n_2^*$	Derived below
Re-Estimated Incremental Sample Size, $\tilde{n}_2'$	Derived below

The re-estimated cumulative final sample size ( $n_2^*$ ) is computed as follows:

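### The primary endpoint's 95% interval uses the null variance up to 90% and Clopper-Pearson above it, so it is miscalibrated away from 80% and its upper limit falls when the result improves

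*SAP*

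**What the plan says.** SAP 8.9 defines the interval for the number and proportion achieving Technical Efficacy at Visit 3 as the normal approximation, a "Z-test that uses S(P0) to estimate the standard deviation) or Clopper-Pearson method (if the proportion is greater than 90%) will be calculated". The same section sets P0 at 80% and declares success if the lower limit of the two-sided interval is above 0.8. It carries the method into both sensitivity analyses.

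Protocol 8.1 has the S(P0) interval without the switch: "If the lower limit of the 95% CI of the Technical Efficacy rate based on the Normal Approximation to the Binomial distribution" exceeds the goal, the endpoint is met. The SAP states that it overrides the protocol's statistical section, so the two-part rule governs.

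Other rates are handled differently. The secondary rates (SAP 8.10.1 to 8.10.4) use S(Phat) with the same 90% switch. The subgroup analyses, which include Technical Efficacy itself (SAP 8.15), use Clopper-Pearson throughout.

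**The concern.** S(P0) is the standard error the observed rate would have if the true rate were exactly 80%. That is the right quantity for a test of 80%, and it matches the sample size calculation and the interim statistic. An interval has to be calibrated at whatever the true rate is. Centred on the observed rate with S(P0), it is too wide when the truth is above 80% and too narrow when it is below. Changing method at 90% then puts a discontinuity where the result is expected to fall.

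This interval is the precision statement for the only hypothesis-tested endpoint, in a report intended for the NMPA. An upper limit that drops when the device does better is hard to defend, and the sponsor would understate its own precision around the rate it expects.

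**Working it through.** **Inputs.** Goal P0 = 0.80 (SAP 7). Rate and error level: "when the expected performance is 90% and a one-sided significance level of 0.025 is used" (SAP 7). Size: "A sample size of 120 subjects is necessary to achieve at least 80% power", "with adjustment for up to 10% dropout" (SAP 7). Evaluable n = 108 as planned (SAP 8.12.1) and 180 at most (SAP 8.12); n = 120 represents no dropout. Observations are taken as independent, and the 90% is read as the observed proportion.

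**1. The plan's own figure.** With the null-variance Z-test,

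n = [(1.960·√(0.8·0.2) + 0.842·√(0.9·0.1)) / 0.10]² = 107.4, rounded up to 108; 108/0.90 = 120.

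The plan's 120 reproduces, with approximate power 0.803 at 108. Using S(Phat) instead gives 71 (79 with dropout), so S(P0) is the test the trial was sized on.

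**2. The three intervals.**
- SAP up to 90%: p̂ ± 1.96·√(0.16/n). At n = 108 the half-width is 1.96·√(0.16/108) = 0.0754 for every p̂.
- Clopper-Pearson (SAP above 90%): the 0.025 quantile of Beta(x, n−x+1) and the 0.975 quantile of Beta(x+1, n−x).
- Wilson: [p̂ + z²/2n ± z·√(p̂(1−p̂)/n + z²/4n²)] / (1 + z²/n).

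| x/n | p̂ | SAP rule | Clopper-Pearson | Wilson |
|---|---|---|---|---|
| 97/108 | 89.8% | 82.3% to 97.4% | 82.5% to 94.8% | 82.7% to 94.2% |
| 98/108 | 90.7% | 83.6% to 95.5% | 83.6% to 95.5% | 83.8% to 94.9% |

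Under the SAP rule the upper limit falls by 97.4 − 95.5 = 1.9 points, and it takes 101/108 to bring it back to about 97.4%. At n = 120 it goes from 97.2% (108 successes) to 95.3% (109). At n = 180 it goes from 95.8% (162) to 94.4% (163). The drop occurs at every n from 30 to 330. The lower limit never drops.

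At 97/108 the SAP interval is 15.1 points wide, against 12.3 for Clopper-Pearson and 11.5 for Wilson. At 95 to 97 of 108 it is 22% to 31% wider than Wilson. Those three counts all pass and together have probability 33% if the true rate is 0.90. At that rate the observed proportion falls on the S(P0) side of the switch 52% of the time and on the Clopper-Pearson side 48%.

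**3. Exact binomial coverage.**

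| True rate | n | SAP rule | Wilson |
|---|---|---|---|
| 0.70 | 108 | 90.8% | 94.2% |
| 0.75 | 108 | 94.2% | 94.2% |
| 0.75 | 120 | 92.8% | 95.6% |
| 0.80 | 108 | 94.7% | 94.7% |
| 0.90 | 108 | 97.6% | 94.6% |
| 0.95 | 108 | 99.5% | 95.2% |

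The S(P0) interval on its own, as in protocol 8.1, covers 98.9% at 0.90 with n = 108.

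**4. The success decision.** The smallest passing counts are 95/108, 105/120 and 155/180 under the SAP rule, Clopper-Pearson and Wilson alike. Exact one-sided type I error is 0.0210, 0.0218 and 0.0217. Power at 0.90 is 0.810 with n = 108. Over all counts for n = 60 to 300, the SAP rule and Wilson disagree only at 55/61.

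**The case against.** Several points can be made for the plan as it stands.

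- *The SAP does not print the formula.* An interval based on a null-variance Z-test could mean the inversion of that test, which is Wilson, and then the upper limit rises at the switch. This reading is strained: P0 is defined in the same section as 80%, and a standard error fixed there is not one re-evaluated at each candidate rate. It does show that the formula should be written out.
- *No binomial interval covers exactly 95%.* This is true. At 0.90 with n = 108, Clopper-Pearson covers 96.5%, only 1.1 points below the SAP rule. Wilson dips below nominal in places (93.9% at 0.90 with n = 180), and at 0.75 with n = 108 it covers no better than the SAP rule. The under-coverage therefore rests on the 0.70 and n = 120 figures. Ordinary discreteness does not explain 90.8% or 99.5%, or an upper limit that falls.
- *The error is mostly on the cautious side.* For true rates of 0.80 to 0.99 at n = 108, coverage is never below 94.7%. Material under-coverage needs a true rate below the goal, where the trial should fail. This stands and limits the weight of the point.
- *Nothing decisional changes.* This also stands. Success uses only the lower limit.
- *Tumours within a subject may be correlated.* No independent-binomial interval deals with that, Wilson included. It is a separate matter and was not examined here.

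**Conclusion.** The interval is wrong as specified. It is calibrated only near a true rate of 80%: too wide at the expected 90% (coverage 97.6% at n = 108) and too narrow below the goal (90.8% at 0.70). Its upper limit falls by 1.9 points at n = 108, and by 1.4 points at n = 180, when one success is added across the 90% line. The fault lies in the reported precision, mainly the upper limit. The test, sample size, type I error, power and success decision are sound at 108, 120 and 180 evaluable. It should be corrected before the primary analysis but does not threaten the trial's conclusion. The result assumes independent observations, the switch applied to the observed proportion, and S(P0) evaluated at 0.80.

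**What to change.** In SAP 8.9, keep the S(P0) Z-test for the decision and report the Wilson score 95% interval at every observed proportion, with the formula written out. Delete the S(P0) interval and the 90% switch, for the primary analysis and both sensitivity analyses. The Wilson lower limit exceeds 0.80 exactly when the S(P0) Z-test rejects, so the success rule can still be stated through the interval and the thresholds stay at 95/108, 105/120 and 155/180. Clopper-Pearson throughout would also remove the drop and keep those thresholds, with slightly wider limits.

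Do not copy the S(Phat) rule from the secondary endpoints. At 94/108 (p̂ = 0.870) its lower limit is 0.870 − 1.96·√(0.870·0.130/108) = 0.807, so 94 would pass and the exact type I error would rise to 0.0388, above 0.025.

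The cost is SAP wording and one line of code, with no extra subjects. Because the SAP takes precedence, that edit is enough to correct the analysis. Protocol 8.1 should be brought into line as well, through the protocol's own amendment process.
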